**Table 11: Summary of Safety Analysis**

Safety Evaluation	Incidence	Raw Value	Change from Baseline	Normal Range Shift from Baseline	Potentially Clinically Significant	Abnormality/ Clinical Significance
Adverse Events	X					
Clinical Laboratory		X	X	X	X	*
Physical Exam		*				
Vital Signs		X	X		X	
ECG		X	X		X	*
[REDACTED]						
ECG = electrocardiogram; [REDACTED] X = Safety Assessment will be summarized in tables * = Safety Assessment will be listed in individual participant data listings						

For safety analysis, unscheduled measurements will be included only if a scheduled measurement is not available, and the unscheduled measurement falls within the visit window for the scheduled visit (Table 12 and Table 13). If there are two or more measurements in a visit window, the measurement taken closest to the study day target will be used in analysis. If the two have same distance from the target study day, the latter one will be used.

**Table 12: Analysis Visit Windows for Safety Analysis – Vital Signs and [REDACTED]**

Scheduled Visit	Study Day of Expected Visit	Study Day Window for Visit
Baseline	1	$\leq 1$
Day 14 ( $\pm 2$ days)	14	2 to 20
Day 28 ( $\pm 2$ days)	28	21 to 42
Day 56 ( $\pm 2$ days)	56	43 to 70
Day 84 ( $\pm 2$ days)	84	71 to 91
Day 98 ( $\pm 2$ days)	98	92 to 105
Day 112 ( $\pm 2$ days)	112	$\geq 105$

**Table 13. Analysis Visit Windows for Safety Analysis – Clinical Laboratory and ECG**

Scheduled Visit	Study Day of Expected Visit	Study Day Window for Visit
Baseline	1	$\leq 1$
Day 28 ( $\pm 2$ days)	28	2 to 56
Day 84 ( $\pm 2$ days)	84	57 to 98
Day 112 ( $\pm 2$ days)	112	$\geq 99$

**Table 14. [REDACTED]**

#### 8.4.1. Adverse Events

Adverse events will be coded using Medical Dictionary for Regulatory Activities (MedDRA) Version 25.1. Intensity/severity and relationship of AE will be evaluated by the investigator.

A TEAE is defined as an AE with onset on or after the first dose of IP or any worsening of a pre-existing medical condition/AE with onset after the start of IP and throughout the study. The analysis of AEs will be based on the concept of TEAEs. Where the AE start date is missing, adverse events will be assumed to be treatment-emergent, unless there is clear evidence (through comparison of partial dates) to suggest that the adverse event started prior

to the first dose of study treatment. Missing or partial dates will be imputed for AE. The algorithm for missing or partial start /end date is documented in [Appendix C](#).

Adverse events are assigned an AE period based on the onset date/time. AE periods are defined as follows:

- Pre-treatment AE: AE onset date before first IP dosing date/time
- TEAE: AE onset date/time on or after the first IP dose date/time (If an AE start date same as IP first dose date, but no time either in AE start or treatment start, then consider this AE to be in treatment period TEAE.)
- On-treatment TEAE: AE onset date/time on or after first IP dose date/time and on or before IP last dose date + 30 days (Note that time does not matter for the end of this period. i.e. if AE occurred after the last dose but on the same date of last dose, it is considered as on-treatment TEAE)
- Post-treatment TEAE: AE onset date on or after IP last dose date + 31 days

An overall summary of TEAEs will include the number and percentage of participants and number of events in the following categories:

- Any TEAEs
- Any TEAEs (On-treatment, Post-treatment)
- TEAEs by maximum Severity (severe>moderate>mild)
- Any related TEAEs
- Any related TEAEs by maximum Severity (severe>moderate>mild)
- Any serious TEAEs
- Any serious related TEAEs
- Any TEAEs leading to death
- Any TEAEs leading to IP dose reduction
- Any TEAEs leading to IP withdrawal
- Any TEAEs leading to withdrawal from the study
- Any TEAEs leading to IP interruption

Incidence of TEAEs in following categories will be provided by SOC and PT. A participant is counted only once under each SOC and PT in case of multiple occurrences of the same AE. These tables will be sorted by decreasing frequency of System Organ Class (SOC) in SAGE-718 group, then in placebo group, then alphabetically first within SOC then within preferred term.

- TEAEs
  - On-treatment TEAEs
  - Post-treatment TEAEs

- TEAEs by maximum Severity
  - On-treatment TEAEs
  - Post-treatment TEAEs
- TEAEs by relationship (related, not related) to IP
  - On-treatment TEAE
  - Post-treatment TEAE
- TEAEs by maximum Severity and relationship (related, not related) to IP
  - On-treatment TEAE
  - Post-treatment TEAE
- Serious TEAEs
- TEAEs leading to IP dose reduction
- TEAEs leading to IP withdrawal
- TEAEs leading to withdrawal from the study
- TEAEs leading to IP interruption

Additionally, incidence of TEAEs will be summarized by PT. Most common TEAEs reported >5% in either treatment group will also be summarized by PT.

For maximum severity, participants will be counted only once within each SOC and PT at the maximum severity in the following order: severe > moderate > mild; an AE with missing severity will be omitted from severity presentation and will not be imputed. For relationship to IP, participant will be counted only once within each SOC and PT at the strongest relationship to IP in the following order: related > not related; an AE with relationship missing is treated as related. For seriousness, an AE with missing seriousness will not be imputed. The incidences will be presented by descending frequency of SOC and then, within a SOC, by descending frequency of PT based on the participant count, and in alphabetical order of PT if the incidence within a PT is a tie.

In addition, TEAE summary by SOC and PT will also be presented by the following subgroups:

- Age group: ≤50, >50 years
- Race (Black or African American, White, Other)
- Sex (Male, Female, Unknown/Undifferentiated)
- BMI ( $\leq 18.4$ , 18.5-24.9, 25-29.9,  $\geq 30$  kg/m^2)
- Country (US, Rest of World)

A by-participant listing of each TEAE category will also be provided. All AEs and SAEs (including those with onset or worsening before the start of IP) through the end of the study, and most frequent (5%) TEAE will be listed.

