### **12.2. Adverse and Serious Adverse Events**

#### **12.2.1. Adverse Event Definition**

An AE is any untoward medical occurrence in a patient or clinical investigation participant administered a pharmaceutical product and that does not necessarily have a causal relationship with this treatment. An AE can therefore be any unfavorable and unintended sign (including an abnormal laboratory finding), symptom or disease temporally associated with the use of a medicinal (investigational) product whether or not related to the medicinal (investigational) product. In clinical studies, an AE can include an undesirable medical condition occurring at any time, including baseline or washout periods, even if no study treatment has been administered.

A treatment-emergent adverse event (TEAE) is defined as an AE with onset after the start of IP, or any worsening of a pre-existing medical condition/AE with onset after the start of IP and

throughout the study. The term IP includes any Sage IP, a comparator, or a placebo administered in a clinical study.

Laboratory abnormalities and changes from baseline in vital signs, and ECGs are considered AEs if they result in discontinuation or interruption of study treatment, require therapeutic medical intervention, meet protocol specific criteria (if applicable) or if the investigator considers them to be CS. Any abnormalities that meet the criteria for an SAE should be reported in an expedited manner. Laboratory abnormalities and changes from baseline in vital signs and ECGs that are clearly attributable to another AE do not require discrete reporting (eg, electrolyte disturbances in the context of dehydration, chemistry, and hematologic disturbances in the context of sepsis).

All AEs that occur after any participant has signed the informed consent and throughout the duration of the study, whether or not they are related to the study, must be reported to Sage Therapeutics.

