### **13.6.1. Adverse Events**

AEs/SAEs will be coded using Medical Dictionary for Regulatory Activities (MedDRA) Version 22.0 or higher. A TEAE is defined as an AE with onset after the first dose of IP. The analysis of AEs will be based on the concept of TEAEs. The incidence of TEAEs will be summarized by System Organ Class (SOC) and Preferred Term (PT). In addition, summaries will be provided by intensity (mild, moderate, severe) and by causality (related, not related) to IP.

Any TEAEs leading to discontinuation of treatment or withdrawal from the study and any treatment emergent SAEs will be summarized.

All AEs and SAEs (including those with onset or worsening before the start of IP) through the end of the study will be listed.

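### SAP 8.4.1 counts post-dose worsening as treatment-emergent but assigns AE periods by onset alone, so an AE that starts before dosing and worsens on IP can be classed as pre-treatment

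*SAP*

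**What the plan says.** SAP 8.4.1 opens with a two-part definition. A TEAE is an AE with onset on or after first dose, or "any worsening of a pre-existing medical condition/AE with onset after the start of IP and throughout the study". It adds: "The analysis of AEs will be based on the concept of TEAEs".

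The same section then gives the rules that a programmer would apply: "Adverse events are assigned an AE period based on the onset date/time". Four periods follow:

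- "Pre-treatment AE: AE onset date before first IP dosing date/time"
- "TEAE: AE onset date/time on or after the first IP dose date/time"
- on-treatment TEAE: onset from first dose up to 30 days after the last dose date
- post-treatment TEAE: onset from 31 days after the last dose date

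None of the four has a worsening clause.

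The protocol is split in the same way. Section 12.2.1 includes worsening: "or any worsening of a pre-existing medical condition/AE with onset after the start of IP". Section 13.6.1, in the statistics chapter, does not: "A TEAE is defined as an AE with onset after the first dose of IP".

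AEs are collected before dosing. Protocol 12.2.1 requires reporting of "All AEs that occur after any participant has signed the informed consent and throughout the duration of the study", and screening assessments run from Day -28 to Day -1. Protocol 12.2.5 lists what is reported for each AE (onset, resolution, intensity and so on). It does not say whether a worsening opens a new record.

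**The concern.** The proportion of participants with TEAEs is the trial's named safety endpoint, under a secondary objective. One section of the SAP gives the term two meanings that are not equivalent, and does not say which one drives the tables.

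The meanings part company for an AE that begins during screening and gets worse on IP. If the onset rule is applied to a record that still carries the screening onset date, the event is sorted with the pre-treatment AEs. The same could happen in the tables of serious TEAEs and of TEAEs leading to dose reduction, interruption or withdrawal. A single participant can matter in tables with few events.

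If the choice of rule is left until someone notices a mismatch, it may be made after the sponsor's restricted team has been unblinded.

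**Working it through.** The plan states no figure to reproduce here, so the check is one of logic.

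**1. Apply both rules to four example records** (days counted from first dose).

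| Record | By the definition | By the period rule | Agree? |
|---|---|---|---|
| New onset 10 days after first dose | TEAE | On-treatment TEAE | Yes |
| Onset 10 days before, no worsening | Not a TEAE | Pre-treatment | Yes |
| Onset 10 days before, worsens 20 days after, one record with original onset | TEAE | Pre-treatment | **No** |
| The same worsening entered as a new record, onset 20 days after | TEAE | On-treatment TEAE | Yes |

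The rules conflict only in the third case.

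**2. Follow the third case into the tables.** On-treatment and post-treatment TEAEs are defined only by onset. SAP 8.4.1 uses that split for TEAE incidence and for the tables by maximum severity, by relationship, and by the two combined. A third-case event is absent from all these sub-tables, whichever meaning drives the overall TEAE row. The serious-TEAE and action-taken tables are not split, so their content depends on which meaning is programmed.

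**3. Check reconciliation.** The overall summary reports numbers of events as well as participants. Let E_on and E_post be the event counts in the two periods, and W the number of third-case events. The cut-points (last dose + 30 days, last dose + 31 days) leave no gap, so E_on + E_post covers every record with onset on or after first dose.

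- Overall row from the period rule: total = E_on + E_post, and W is missing.
- Overall row from the definition: total = E_on + E_post + W, which exceeds the two rows by W.

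This applies to event counts. Participant counts need not add up in any case, because one person can appear in both periods.

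**4. Look for a worsening date elsewhere.** The missing-start-date default in SAP 8.4.1 turns on whether the event started before first dose. SAP Appendix C, which is written in part to classify TEAEs, imputes start dates and uses end dates as a check. Neither mentions a date of worsening.

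**5. Scale of the effect on the endpoint.** A participant's TEAE status changes only if the missed worsening is that person's sole TEAE. With the planned 89 randomized per arm, and assuming all are dosed, each such participant moves the arm's proportion by 1/89 = 1.1 percentage points. The documents give no count of such participants.

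**The case against.** The best defence is that the text can be read consistently. The definition can be taken to give the worsening its own onset, in which case the onset date/time in the period rules could be the date of worsening. The sentence tying the analysis to the TEAE concept comes after the full definition, and nothing says the period rules override it. Protocol chapter 13 also defers detail to the SAP, whose definition restores what 13.6.1 leaves out. This reading is available, but it needs a recorded date of worsening, and neither document names one. It therefore shows that the conflict can be cured by wording, not that the wording is already clear.

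The second defence is that recording practice may remove the problem. The SAP rests on eCRF version 12.0, which is not among the documents. Its instructions may already require a new record when an AE worsens, and then the onset rule counts the event. This stands, and it is why loss cannot be called certain.

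The third defence narrows the events at issue. Motor, psychiatric or cognitive symptoms present before consent belong to medical history. If one worsens on IP there is no earlier AE record, and the natural entry is an AE dated at the worsening, which is counted. This also stands. The firm exposure is limited to AEs that start between consent and first dose, are still present at dosing, worsen, and are not re-entered.

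Finally, all AEs remain in the participant listings, and SAEs are reported from consent onward. The SAP plans no hypothesis tests on safety data. This limits the harm, but listings do not feed the TEAE proportions.

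**Conclusion.** The inconsistency is real and should be corrected before lock. The SAP's period rules conflict with its own TEAE definition for one identifiable type of record, and protocol 13.6.1 disagrees with 12.2.1 on the same point. For such a record, omission from the on- and post-treatment tables follows from the text. Omission from the overall TEAE count follows only if that count is programmed from the period rule; otherwise the event totals do not reconcile.

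A reader might infer that worsened pre-dose events are certain to vanish from every TEAE table and that the TEAE proportions will be too low. The documents do not support that. It requires both that the event keeps its original record and onset and that the period rule drives the overall count, and the documents settle neither. Nor do they support a claim that the severity tables suffer most, or that worsening of long-standing Huntington's symptoms is generally missed.

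The number affected cannot be computed. Any percentage would need the rate of pre-dose AEs, the share that worsen on IP, and the share not re-entered, and none of these is given. Efficacy and sample size are not affected.

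**What to change.** 1. In SAP 8.4.1, assign the AE period by onset date/time or, for an AE present before first dose, by the date of its first worsening after first dose. Apply this to the TEAE, on-treatment and post-treatment rules, and state that the overall TEAE rows use the same rule.
2. Bring the TEAE definition in protocol 13.6.1 into line with 12.2.1.
3. Unless the eCRF instructions already do so, state in protocol 12.2.5 and those instructions that a post-dose worsening is entered as a new AE record dated at the worsening.
4. While still blinded, review AEs with pre-dose onset that were ongoing at first dose, and query any that may have worsened. Do this before the Part 1 lock, because SAP 5.4 unblinds a restricted sponsor team after it.

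The cost is a few lines of wording and a short query list. TEAE proportions may rise slightly.

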#### 8.4.2. Clinical Laboratory

Clinical laboratory assessments will include blood samples for hematology, clinical chemistry, coagulation, and urinalysis. Samples will be collected  $\leq 2$  hours prior to dosing on dosing days. On non-dosing days, collection may occur at anytime.

Any lab results considered clinically significant by the investigator will be captured as adverse events, hence will show up in AE displays.

All laboratory values will be summarized for the Safety Set using actual treatment received. Results of continuous hematology, clinical chemistry parameters, coagulation, and urinalysis parameters (quantitative) at each scheduled visit and mean changes from baseline will be summarized using standard international (SI) units. In addition, it will also include the summary of last post-baseline values on treatment (on or after first dose, on or before last dose) and on study (on or after first dose, on or before last day of the study).

All laboratory results will be listed in individual participant data listings.

Normal ranges for each parameter will be provided by the laboratory. Shift from baseline to worst post-baseline values in abnormality of results at anytime on treatment, the last value on treatment (on or after first dose, on or before last dose and the last value on study (on or after first dose, on or before last day of the study) in abnormality of results will be summarized. If a participant has both low and high post-baseline records, the participant will be counted twice for each low and high cell.

The number and percentage of participants with potentially clinically significant (PCS) values will be provided in separate displays in hematology, clinical chemistry and liver function tests provided for such occurrence for anytime on treatment, last value on treatment, within 28 Days after the last dose of treatment (follow-up period). PCS values will be identified for specific laboratory parameters as outlined in the table below.

Liver function tests will be monitored closely for PCS values, and will be summarized for occurrence anytime post-baseline for the following parameters for these PCS threshold (for condition involving more than one parameter, the results need to be from the same timepoint):

- Alanine Aminotransferase:  $>3\times\text{ULN}$ ,  $>5\times\text{ULN}$ ,  $>10\times\text{ULN}$
- Aspartate Aminotransferase:  $>3\times\text{ULN}$ ,  $>5\times\text{ULN}$ ,  $>10\times\text{ULN}$
- Alanine Aminotransferase or Aspartate Aminotransferase:  $>3\times\text{ULN}$ ,  $>5\times\text{ULN}$ ,  $>10\times\text{ULN}$
- Alkaline Phosphatase:  $>1.5\times\text{ULN}$ ,  $>2\times\text{ULN}$
- Total Bilirubin:  $>1.5\times\text{ULN}$ ,  $>2\times\text{ULN}$
- Total Bilirubin  $>2\times\text{ULN}$  AND (Alanine Aminotransferase or Aspartate Aminotransferase  $>3\times\text{ULN}$ ) [any time post-baseline, does not need to be measured at the same time point of assessment]

- Total Bilirubin  $>2 \times \text{ULN}$  AND Alkaline Phosphatase  $<2 \times \text{ULN}$  (any time post-baseline, measured at the same time point of assessment)] AND [(ALT or AST  $>3 \times \text{ULN}$ ) AND Alkaline Phosphatase  $<2 \times \text{ULN}$ , any time post-baseline, measured at the same time point of assessment]

*Note:* The conditions in the first pair of brackets do not need to occur at the same timepoint as the conditions in the second pair of brackets.

Any lab results considered clinically significant by the investigator will be captured as adverse events, hence will show up in AE displays.

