During the Treatment Period, participants will be able to receive IP as long as there are no dose limiting safety/tolerability concerns. Participants who cannot tolerate 1.2 mg will receive 0.9 mg for the remainder of the Treatment Period. At the discretion of the investigator, participants who cannot tolerate the 0.9 mg dose will be discontinued from IP. Participants who discontinue IP early should complete the remaining study visits as scheduled unless the participant withdraws consent or loses the capacity to grant consent. If a participant withdraws from the study/stops study participation early, an early termination (ET) visit should be conducted. Treatment with SAGE-718 can be ended without down titration.

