### **7.1.2. Treatment Period**

Eligible participants will be randomized 1:1 to receive either SAGE-718, or placebo for 84 days. Beginning on Day 1 and continuing through the 12-week treatment period, participants will self-administer SAGE-718 or placebo once per day in the morning. Participants who utilize the  $\pm 2$ -day window at Day 84 should continue to self-administer IP within the visit window. IP administration will be monitored using the [REDACTED].

At clinic visits, participants will take the IP under staff supervision, followed by assessments of cognitive function, [REDACTED] as outlined in [Table 2](#) and [Figure 1](#). Study staff will dispense sufficient IP for daily administration until the next scheduled study visit. Adherence to the dosing regimen will be assessed at each in-clinic visit by review of the medication adherence monitoring platform, examination of the used packaging, and counting any returned tablets. [REDACTED]  
[REDACTED]  
[REDACTED]

[figure not shown]

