### **7.1.3. Follow-up Period**

Follow-up period starts after Day 84 and continuing through Day 112. After completing the Treatment Period, participants will return to the clinic for follow-up visits on Days 98 and 112 (or ET) to collect continued safety and efficacy data.

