### **8.4.1. Investigational Product Discontinuation**

Participants who discontinue IP will be invited by the investigator to complete all of the scheduled study visits and assessments through the end of the Treatment Period. Those who decline to continue participation will be asked to complete an ET Visit.

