#### 8.4. Safety Analysis

Safety and tolerability of SAGE-718 is a secondary objective of this study. Proportion of participants experienced treatment-emergent adverse events (TEAEs) is one of the secondary endpoints, and change from baseline in vital signs, clinical laboratory analyses, electrocardiograms (ECGs), [REDACTED]

[REDACTED] (Table 11). All safety analysis will be performed on the Safety Set using actual treatment received.

The safety endpoints evaluated at scheduled visits within treatment period are taken as done in nominal visit, without any windowing. If a value is available for a nominal scheduled visit, that value will be used in summary by visit. If scheduled visit value is not available, a value from the specific visit window will be included in summary. For Post-treatment period visits, the choice of the visit will follow the same rule as described in Table 12 and Table 13.

Anytime on treatment, last value on treatment and last value on study will be included in the summaries whenever indicated in the relevant sections below. Anytime on treatment is defined as measurement on or after first dose, on or before the date of last dose. Last value on treatment is defined as the last post-baseline value between first dose of IP (exclusive) and up to the date of last dose of IP (inclusive). Last value on study is defined as the last post-baseline value on or after the first dose of IP and on or before the last date of the study.

No statistical hypothesis testing will be conducted on the safety analyses.

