#### 8.4.3. 12-Lead Electrocardiogram

A single 12-lead ECG under Protocol Amendment 2 and triplicate 12-lead ECG under Original Protocol and Protocol Amendment 1 will be performed after the participant has been resting in the supine position for at least 5 minutes. If the multiple 12-lead ECG are performed, the average of all values on the same date will be used in the summary. If there are both scheduled visit and unscheduled visit on the same date, all the assessments on that date are considered as the scheduled visit for the summary. A summary of the observed values (raw values for the single ECG; average values for the multiple ECG on the same date) and change from baseline values will be summarized by each scheduled visit for the following ECG parameters: heart rate, PR, QRS, QT, and QTcF interval. This summary will also include the last values on treatment and on study. A by-participant listing of 12 lead ECG will also be provided for each of the ECG measurements.

Each ECG is evaluated as ‘normal’, ‘abnormal, not clinically significant’ and ‘abnormal, clinically significant’. The number and percentage of participants with the categories of

‘abnormal, clinically significant’ and ‘abnormal, not clinically significant’ from the latest triplicated ECG value will be provided at baseline and each post-baseline scheduled assessment time point.

Potentially clinically significant values of QTcF as outlined in the table below will be summarized by treatment for anytime on treatment, last value on treatment, within 28 Days after the last dose of treatment (follow-up period). This analysis includes triplicate values individually and is not based on average value. Electrocardiogram findings will be listed by participant and visit.

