#### 8.4.4. Vital Signs

Vital signs will include oral temperature(°C), respiratory rate (breaths per minute), heart rate (beats per minute [bpm]), and blood pressures (mmHg). Heart rate and blood pressure were collected in supine position and standing position at all scheduled time points.

Vital sign results and mean changes from baseline will be summarized by scheduled visit. It will also include the summary of last values on treatment and on study assessments.

Potentially clinically significant values as outlined in the table below will be summarized by treatment and for anytime on treatment, last value on treatment, within 28 Days after the last dose of treatment (follow-up period). By-participant listing of vital signs will also be provided.

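### The 28-day follow-up row for PCS values can leave out a compliant Day 112 visit, and the non-liver PCS tables have no row for late values of participants who stop drug early and stay

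*SAP*

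**What the plan says.** The three PCS sections of the SAP use the same periods. For laboratory tests (8.4.2) the off-treatment period is "within 28 Days after the last dose of treatment (follow-up period"). For QTcF (8.4.3) PCS values are "summarized by treatment for anytime on treatment, last value on treatment, within 28 Days after the last dose of treatment (follow-up period"), and the vital-sign text (8.4.4) has the same three periods.

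SAP 8.4 closes the first period at the last dose: "Anytime on treatment is defined as measurement on or after first dose, on or before the date of last dose". The last value on treatment has the same end date. The SAP does not define the follow-up period. Protocol 7.1.3 does, in terms of the visit schedule: "Follow-up period starts after Day 84 and continuing through Day 112".

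The schedule of assessments allows ±2 days at Day 84 and at Day 112. Protocol 7.1.2 says that participants who use the Day 84 window "should continue to self-administer IP within the visit window", and note v to the schedule has Day 84 dosing done in the clinic. Laboratory tests and ECGs are scheduled after Day 1 at Days 28, 84 and 112 only (schedule; SAP Table 13). Vital signs are also taken at Days 14, 56 and 98.

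Participants who stop drug are asked to stay. Protocol 7.1 states: "Participants who discontinue IP early should complete the remaining study visits as scheduled". Protocol 8.4.1 is narrower: they are "invited by the investigator to complete all of the scheduled study visits and assessments through the end of the Treatment Period". Day 84 is covered by both.

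For liver tests, SAP 8.4.2 has a further PCS summary covering any time post-baseline, with no cut-off from last dose.

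**The concern.** The 28 days appear to have been taken from the nominal distance between Day 84 and Day 112, with no allowance for visit windows. A participant who complies fully with the protocol can then have a Day 112 value that falls outside the row that seems meant for it. The added label in parentheses makes this worse: one programmer may apply the 28 days and another may take the scheduled follow-up visits, and their counts would differ.

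A second gap arises because the protocol asks early stoppers to keep attending. Their later values come after the last dose, so neither on-treatment row takes them, and many come more than 28 days after it.

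In the visible text, these tables are the only planned counts of participants against the fixed non-liver laboratory, QTcF and vital-sign thresholds (SAP Tables 15 to 17). What is at stake is whether those counts are complete and reproducible.

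**Working it through.** **Reproducing the 28 days.** Nominal Day 112 minus nominal Day 84: 112 − 84 = 28.

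**Completers.** Inputs: last dose on the day of the Day 84 visit, Days 82 to 86; Day 112 visit on Days 110 to 114. Gap = Day 112 visit day − last dose day.

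| Last dose | Visit 110 | 111 | 112 | 113 | 114 |
|---|---|---|---|---|---|
| Day 82 | 28 | 29 | 30 | 31 | 32 |
| Day 83 | 27 | 28 | 29 | 30 | 31 |
| Day 84 | 26 | 27 | 28 | 29 | 30 |
| Day 85 | 25 | 26 | 27 | 28 | 29 |
| Day 86 | 24 | 25 | 26 | 27 | 28 |

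Gaps run from 24 to 32 days. Gaps above 28: 4 + 3 + 2 + 1 + 0 = 10 of 25. All 25 are at most 32. For vital signs the Day 98 visit stays inside the row (largest gap 100 − 82 = 18), so only Day 112 is at risk. For laboratory tests and ECG there is no Day 98 visit, so an excluded Day 112 visit leaves the row with no scheduled value.

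**Early stoppers who stay.** The 28-day row misses a visit on day V when V − L ≥ 29, where L is the last dose day. The on-treatment rows miss it because V > L.

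- Day 84 visit on target: 84 − L ≥ 29 gives L ≤ 55. Example: last dose Day 55, gap 29.
- Day 84 visit anywhere in its window, earliest Day 82: 82 − L ≥ 29 gives L ≤ 53. With last dose on Day 55, a visit on Day 82 or 83 has a gap of 27 or 28 and is counted.
- Day 56 vital signs on target: 56 − L ≥ 29 gives L ≤ 27. Anywhere in the window, earliest Day 54: L ≤ 25.

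**Would a longer follow-up row alone be enough?** With a 32-day limit, an on-target Day 84 value is still missed when 84 − L ≥ 33, that is L ≤ 51. Early stoppers therefore need a separate row.

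**Side check on SAP Table 12.** The Day 98 window is 92 to 105 and the Day 112 window is ≥105, so Day 105 is in both. It is equally far from each target (105 − 98 = 7; 112 − 105 = 7).

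**The case against.** The strongest reply is that the SAP states an operative rule, 28 days from last dose, and that the parenthesis only labels it. On that view there is no contradiction, just a cut-off, and nothing in SAP 8.4.2 to 8.4.4 points to Protocol 7.1.3. This is a fair reading, and the point does not need a contradiction: the rule taken at its words is what drops the 10 day pairs.

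A reader might infer that the protocol's definition would rescue every Day 112 visit. That holds only if Protocol 7.1.3 is read by nominal visit. Read by study day, visits on Day 113 or 114 fall outside it, which is 2 × 5 = 10 of the 25 pairs, and 7 of those also exceed 28 days. A third reading, all time after each participant's own last dose, would take the early stoppers' values but sets aside the words on 28 days. The SAP does not say which is meant.

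It can also be said that restricting PCS counts to a short time after dosing is coherent, and that a value 29 to 83 days after last dose says little about the drug. This stands as a reason not to pool such values into the follow-up row. It is no reason to give them no row, since the SAP already counts liver tests without a cut-off.

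Finally, the values are not lost. They appear in listings, in by-visit and last-value-on-study summaries, and in the laboratory shift tables (last value on study). Abnormal ECGs are counted at each scheduled time point, and abnormalities judged clinically significant become adverse events (Protocol 12.2.1; SAP 8.4.2). This stands in full and sets the severity.

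**Conclusion.** The point holds in limited form, at minor severity.

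- For completers, the 28-day row excludes a compliant Day 112 visit in 10 of 25 permitted day pairs. A reader might take this as 40% of participants. It is not: the documents do not say how visits are spread over the windows.
- For early stoppers who stay, on-target Day 84 non-liver laboratory, QTcF and vital-sign values have no PCS row if last dose was on or before Day 55 (Day 53 for any in-window visit). On-target Day 56 vital signs have none if last dose was on or before Day 27. The number of such participants cannot be derived from the documents.
- A reader might infer that the gap extends to liver safety. It does not, for ALT, AST, alkaline phosphatase and total bilirubin.
- Nor does it touch the adverse-event endpoint, and SAP 8.4 plans no safety hypothesis test.

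The result assumes that a completer's last dose is on the Day 84 visit day, that visits are inside their windows, and that early stoppers attend the visits in question.

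**What to change.** In SAP 8.4.2, 8.4.3 and 8.4.4:

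- **(a)** Define the PCS follow-up row so that it includes the scheduled Day 112 visit within its permitted window. Either run it from after the last dose through last dose + 32 days, which takes all 25 pairs, or define it for completers by nominal follow-up visit.
- **(b)** Add a row for any time post-baseline through the last day on study to the non-liver laboratory, QTcF and vital-sign PCS tables, as is already done for liver tests. This also takes a Day 112 visit held outside its window. Add a note that early stoppers contribute longer off-drug observation: up to 112 − 1 = 111 days on target, against at most 32 for completers with in-window visits. Comparisons between arms should be read with that in mind.
- **Minor:** in Table 12, start the Day 112 window at Day 106.

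The cost is a wording change and one extra row per PCS table, from data already collected. No adverse-event count, endpoint or test changes.
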